#### **4.4.2 Data Collection and Follow-up for Withdrawn Subjects**

Participants who elect to discontinue the hormone protocol or are discontinued for safety reasons will be asked to continue to complete self-report ratings through the end of the proposed study period. However, fMRI exams will not be done if participants discontinue the hormone protocol.

## 5 Study Drug

### 5.1 Description

Drug	Dosage	Formulation
Estradiol	100 micrograms/day	Transdermal
Progesterone	200 miligrams/day	Oral capsule

### 5.2 Treatment Regimen

#### Regimen

Once determined eligible and physically well, participants will receive transdermal estradiol (100 µg/day) for 3 weeks. Women will receive an additional week of combined estradiol and micronized progesterone (200 mg/day) at the end of the study to precipitate menstruation.

### 5.3 Method for Assigning Subjects to Treatment Groups

This is a case-control study design, and all subjects will receive the same drug protocol.

### 5.4 Preparation and Administration of Study Drug

All study drugs will be stored, prepared and dispensed from the UNC Investigational Drug Service (IDS).

### 5.5 Subject Compliance Monitoring

We will monitor participants' compliance with the drug regimen by assaying blood levels of estradiol collected at weekly study visits. The drug protocol will be reviewed at each study session, and participants who are significantly non-compliant with the study treatment regimen will be discontinued from the study.

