**Hormone Administration.**

In the OBGYN visit, women will have a basic lab panel and serum pregnancy test performed, and FSH and LH will be assayed. Prior to estradiol administration women will receive a pelvic exam, breast exam and Papanicolaou test. Participants who can provide record of a pelvic exam within the past year and a normal pap results within the past 3 years will be permitted to decline the GYN exam and. Women will be seen in the clinic each week during estradiol administration to assess blood levels of estradiol and mood symptoms. Women will receive an additional week of combined estradiol and micronized progesterone (200 mg/day) at the end of the study to precipitate menstruation. Blood will be batched until the end of data collection, at which point estradiol will be assayed.

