### **5.9.3 Dispensing of Study Drug**

Drugs will be dispensed in tight, light-resistant containers as defined n the USP, with a child-resistant closure. Regular study drug reconciliation will be performed to document drug assigned, drug consumed, and drug remaining. This reconciliation will be logged on the drug accountability form, and signed and dated by the study team.

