### 7.3 Subject Population(s) for Analysis

Given that we are interested in understanding the effect of estradiol on brain function, only data from protocol-compliant participants will be subjected to the study analysis.

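### Compliance is to be monitored by estradiol assays that are run only after data collection ends, so any assay-based exclusion from the compliant-only analysis set would be made late and without a pre-set rule

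*Combined protocol and SAP*

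**What the plan says.** All references are to the combined protocol and SAP.

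- **Section 5.5** makes the assay the compliance tool: compliance is monitored by "assaying blood levels of estradiol collected at weekly study visits". Its next sentence adds a second route and a consequence: "The drug protocol will be reviewed at each study session, and participants who are significantly non-compliant with the study treatment regimen will be discontinued".
- **Section 6, Venipuncture**, gives compliance as the reason for the blood draws after screening.
- **Section 3.1, Hormone Administration**, says of the weekly visits: "Women will be seen in the clinic each week during estradiol administration to assess blood levels of estradiol and mood symptoms". The same paragraph ends: "Blood will be batched until the end of data collection, at which point estradiol will be assayed".
- **Section 5.9.3** provides a record that does not depend on the assay: "Regular study drug reconciliation will be performed to document drug assigned, drug consumed, and drug remaining".
- **Section 7.3** sets the only analysis population: "only data from protocol-compliant participants will be subjected to the study analysis". The reason given is interest in what estradiol does to brain function.
- **Section 4.4.2** allows no further fMRI once a woman stops hormones, but asks her to continue self-report ratings.
- **Section 5.8** marks blinding as not applicable.

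No section gives an estradiol threshold, defines significant non-compliance or protocol compliance, sets a date for fixing the analysis set, or provides an analysis of everyone with data.

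**The concern.** A monitoring tool that can lead to discontinuation has to report while the woman is still in the study. Under Section 3.1 the estradiol result arrives after her last scan and mood rating. The assay can then affect the study only through Section 7.3, by deciding whose completed data are analysed.

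Two things are at stake. First, an exclusion rule written after the outcomes are collected, by people who may have access to them, leaves room for choices that depend on the results. Second, Section 7.3 makes no distinction between hypotheses. H1a and H2a compare the groups at baseline, before any estradiol is given. Selecting those women on later adherence serves no purpose, and it can bias the comparison if adherence differs between women with depression and controls.

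**Working it through.** **Timing.** Table 1 places the second fMRI and the last mood ratings at visit 6. Section 3.1 places the assay after data collection for the study as a whole.

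| Compliance information | Source | Available during participation? |
|---|---|---|
| Estradiol level | 5.5, 6, 3.1 | No, if blood is batched |
| Review at each session | 5.5 | Yes |
| Drug reconciliation | 5.9.3 | Yes |

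Section 5.5 can be read in two ways. If samples are assayed as they are collected, it contradicts Section 3.1. If they are only collected weekly and assayed later, the assay cannot support discontinuation and can act only on the analysis set.

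The choice also changes the data. A woman identified during treatment and discontinued has no second scan (Section 4.4.2). A woman identified from batched blood has a completed second scan that is then dropped.

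**Power: the plan's own figure.** Section 7.1 gives 20 per group, effect size d = 0.9 on change scores and 80% power. It does not state alpha or sidedness, so two-sided 0.05 is assumed.

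- Normal approximation: Φ(d√(n/2) − 1.96) = Φ(0.9 × √10 − 1.96) = Φ(0.886) = 81.2%.
- Noncentral t with 2n − 2 = 38 degrees of freedom and noncentrality 0.9 × √10 = 2.846: 79.2%.

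Both agree with the stated 80%. One-sided versions give 88.5% and 87.5%, so the two-sided assumption is the one that fits.

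**Power after exclusions.** Section 7.1 enrols 10 extra women for attrition, 50 in total. With an even split (assumed) that is 25 per group. Noncentral t, d = 0.9:

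| Analysed per group | Power | Effect detectable with 80% power |
|---|---|---|
| 25 | 87.7% | 0.81 |
| 23 | 84.7% | 0.85 |
| 21 | 81.2% | 0.89 |
| 20 | 79.2% | 0.91 |
| 18 | 74.6% | 0.96 |
| 16 | 69.3% | 1.02 |

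Losing 2 to 4 women per group from 25 leaves 23 to 21 and keeps power at 84.7% to 81.2%. The rows below 20 apply only when dropout plus compliance exclusions exceed 5 per group. The documents give no non-compliance rate, and the allowance is described as covering attrition only.

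**What a late choice of cut-off could do.** This is an illustration under assumptions: no true group difference, 20 per group, estradiol unrelated to outcome, 20,000 simulated studies, and the women with the lowest estradiol in the pooled sample excluded. A study counts as positive if any permitted cut-off gives p < 0.05.

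| Cut-offs available | False-positive rate |
|---|---|
| None excluded, no choice | 5.2% |
| 3 (0, 10, 20% excluded) | 7.9% |
| 7 (0 to 30% in steps of 5) | 10.2% |

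Nothing in the documents says a cut-off would be chosen this way. They contain no rule that would prevent it.

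**The case against.** The case on the other side has real force.

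- A reader might infer that the discontinuation rule cannot operate at all. The text does not support that. In Section 5.5 the discontinuation clause shares its sentence with the session review, and drug reconciliation also runs during the study. Only the assay-based part is disabled.
- A reader might infer that women will be removed from the analysis on their estradiol levels. Section 7.3 does not mention the assay, so this is a possibility left open and not a stated plan. The end of data collection also means that outcomes have been collected, not that anyone has analysed them. A cut-off written in advance and applied without sight of results would remove the risk, but none is given.
- A reader might infer that losing a few women to late assays takes power to about 70%. That ignores the attrition allowance. The plan also expects less attrition than the 12-month trial it cites, which lost under 20%, while granting that depressed women may drop out more.
- Restricting to compliant women has a stated rationale, and Section 1.1 describes the study as providing pilot data. That supports keeping the compliant-only set. It does not justify making it the only set, and it does not extend to comparisons made before treatment.
- Sections 4.4.1 and 8.5 provide for dose titration, so a titrated woman is arguably following the protocol. That is a fair reading, but Section 7.3 leaves it unstated.

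**Conclusion.** The contradiction over when estradiol is assayed is plain on the page. Under batching, the assay cannot contribute to compliance decisions during participation. Session review and drug reconciliation can. Any assay-based exclusion under Section 7.3 would follow collection of all outcomes, in an open-label study, with no cut-off, no separation from the results and no all-participants analysis to set beside it. Applying the restriction to H1a and H2a has no rationale. Whether it would bias them depends on adherence differing by group, for which the documents give no figure.

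The power consequence is conditional. Power stays above 80% while exclusions and dropout together are at most 4 per group, and is 79.2% when the allowance is exactly used up. It falls to 74.6% at 18 and 69.3% at 16 per group only beyond that. These figures assume two-sided 0.05 and, for the allowance, an even split of 50. The stated sample size itself reproduces and is not in dispute.

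This should be fixed. It does not invalidate the design, but an outcome-independent rule can no longer be assured once the assays have been opened alongside the results.

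**What to change.** 1. **Reconcile Sections 3.1, 5.5 and 6** on when estradiol is assayed and what in-study compliance decisions rest on. Which way to settle this is for the sponsor to decide.
2. **In Section 7.3, separate the hypotheses.** Analyse the baseline comparisons (H1a, H2a) in all eligible women with usable baseline data. Analyse the change hypotheses in all women with the relevant outcome data, whatever their assay result and including women whose dose was titrated. Keep the available symptom ratings from women who stop hormones. Do not require both scans for every analysis, because that would discard valid baseline and symptom data.
3. **Report the compliant-only set alongside.** Define protocol compliance in writing, fix the estradiol cut-off before the assays are opened, and have it applied by someone without access to imaging or symptom results.

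The cost is wording in these sections and one extra analysis. The all-participants estimate may be slightly diluted by less-adherent women. One limit remains: because Section 4.4.2 stops fMRI when hormones stop, the analysis of change in activation will still exclude women who discontinue. The report should say so.

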### 5.6 Prior and Concomitant Therapy

Women are required to be free of medications that have known CNS effects to enroll in this study; however, prior medication usage will not preclude participation in the study.

### 5.7 Packaging

The UNC Investigational Drug Service will receive the active drug from their Pharmacy storeroom and will provide the capsules for blinding. Estradiol patches will be provided to participants at weekly study visits. The patches release estradiol for a week. Progesterone capsules will be provided to participants at the final study visit.

### 5.8 Blinding of Study Drug (if applicable)

N/A

## **5.9 Receiving, Storage, Dispensing and Return**

The UNC Investigational Drug Service will receive the study drugs from the UNC Pharmacy Storeroom and will dispense the drug to the PI or research coordinator to deliver to participants. Any unused drug will be returned to the UNC Investigational Drug Service by the PI or research coordinator.

### **5.9.1 Receipt of Drug Supplies**

Upon receipt of the of the study treatment supplies, an inventory will be performed and a drug receipt log filled out and signed by the person accepting the shipment. The designated study staff will count and verify that the shipment contains all the items noted in the shipment inventory. Any damaged or unusable study drug in a given shipment (active drug or comparator) will be documented in the study files. The investigator will notify the UNC Pharmacy Storeroom of any damaged or unusable study treatments that were supplied to the Investigational Drug Service.

### **5.9.2 Storage**

Estradiol and Progesterone will be stored at 20° to 25° C in a temperature-controlled facility.

### **5.9.3 Dispensing of Study Drug**

Drugs will be dispensed in tight, light-resistant containers as defined n the USP, with a child-resistant closure. Regular study drug reconciliation will be performed to document drug assigned, drug consumed, and drug remaining. This reconciliation will be logged on the drug accountability form, and signed and dated by the study team.

### **5.9.4 Return or Destruction of Study Drug**

At the completion of the study, there will be a final reconciliation of drug shipped, drug consumed, and drug remaining. This reconciliation will be logged on the drug reconciliation form, signed and dated. Any discrepancies noted will be investigated, resolved, and documented prior to return or destruction of unused study drug. Drug destroyed on site will be documented in the study files.

## **6 Study Procedures**

The flowchart outlining the procedures at each study visit it attached.

### OBGYN Exam

Participants will receive a gynecological exam prior to drug administration to rule out exclusionary health problems. Results of the exam will be added to participants' UNC Hospital medical record. However, participants who can provide documentation of a normal gynecological exam within the last year will not receive the gynecological exam.

### Venipuncture

Participants will undergo venipuncture at 5 study visits. Initial blood tests will include a pregnancy test, FSH, LH, BUN, creatinine, and a hepatic panel to rule out exclusionary health problems. Lab results will be added to participants' medical records. Subsequent venipuncture will be for the purpose of assaying estradiol levels to ensure participant compliance.

### Drug Administration

Participants will receive estradiol at study visits 3-5. Participants will receive Progesterone at visit 6.

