	
Dose:
 
  
 Drug	Dosage	Formulation	
   
 Estradiol	100 micrograms/day	Transdermal	
 
 Progesterone	200 miligrams/day	Oral capsule	
  
 
Route:
 
  
 Drug	Route of Administration	
   
 Estradiol	Transdermal	
 
 Progesterone	Oral	
  
 
Regimen: Once determined eligible and physically well, participants will receive transdermal estradiol (100 µg/day) for 3 weeks. Prior to estradiol administration women will receive a pelvic and breast exam and Papanicolaou test. Participants who can provide record of a pelvic exam within the past year and normal pap results within the past 3 years will be permitted to decline the GYN exam. Women will also have a basic lab panel and serum pregnancy test performed, and FSH and LH will be assayed. Women will be seen in the clinic each week during estradiol administration to assess blood levels of estradiol and mood symptoms. Women will receive an additional week of combined estradiol and micronized progesterone (200 mg/day) at the end of the study to precipitate menstruation.
	Drug	Dosage	Formulation	Estradiol	100 micrograms/day	Transdermal	Progesterone	200 miligrams/day	Oral capsule	Drug	Route of Administration	Estradiol	Transdermal	Progesterone	Oral
Drug	Dosage	Formulation														
Estradiol	100 micrograms/day	Transdermal														
Progesterone	200 miligrams/day	Oral capsule														
Drug	Route of Administration															
Estradiol	Transdermal															
Progesterone	Oral															
Duration of administration	3 weeks															
Reference population	Perimenopausal women, non-depressed															

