### ESTRADIOL

#### Description

Climara®, estradiol transdermal system, is designed to release estradiol continuously upon application to intact skin. Six (6.5, 9.375, 12.5, 15, 18.75 and 25 cm^2) systems are available to provide nominal *in vivo* delivery of 0.025, 0.0375, 0.05, 0.06, 0.075 or 0.1 mg respectively of estradiol per day. The period of use is 7 days. Each system has a contact surface area of either 6.5, 9.375, 12.5, 15, 18.75 or 25 cm^2, and contains 2, 2.85, 3.8, 4.55, 5.7 or 7.6 mg of estradiol USP respectively. The composition of the systems per unit area is identical. Estradiol USP is a white, crystalline powder, chemically described as *estra-1,3,5(10)-triene-3, 17β-diol*. It has an empirical formula of C18H24O2 and molecular weight of 272.39. The structural formula is:

The Climara system comprises three layers. Proceeding from the visible surface toward the surface attached to the skin, these layers are (1) a translucent polyethylene film, and (2) an acrylate adhesive matrix containing estradiol USP. A protective liner (3) of siliconized or fluoropolymer-coated polyester film is attached to the adhesive surface and must be removed before the system can be used.

The active component of the system is estradiol. The remaining components of the system (acrylate copolymer adhesive, fatty acid esters, and polyethylene backing) are pharmacologically inactive.

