The relationship between estrogen, both endogenous and exogenous, and the development of endometrial carcinoma has been suggested by several different lines of investigation. Numerous retrospective case control studies published since 1975 have indicated that post-menopausal exposure to unopposed estrogens for more than one year results in a two to 12 fold increased relative risk for endometrial cancer. A relationship between the dose and duration of estrogen use and the risk for endometrial cancer has also been shown, the risk being increased after one to four years of estrogen use and rising also with the dosage employed. However, the addition of progesterone to estrogen replacement therapy appears to decrease the risk of endometrial hyperplasia and endometrial cancer to equal or below that of women receiving no hormonal treatment. Recent studies suggest that the optimal regimen to prevent hyperplasia during long term ERT and thus, inferentially, the risk of carcinoma, consists of 12 to 13 days of progesterone treatment each month when estrogens are administered. There is an increase in thromboembolism in women receiving non-contraceptive estrogen therapy. Additionally, some but not all studies report an increase in risk of stroke in older women taking estrogen therapy. However, these complications are unlikely at the dose and duration of estrogen replacement employed in this protocol, and in the younger age group of women who participate in this study. One study reported no effect of the estrogen patch on the four clotting indices previously shown to be altered by oral contraceptive use. Blood pressure, on average, appears to be unaffected by estrogen therapy, although both increases and decreases have been reported. In observational studies, post-menopausal estrogen therapy has been observed to lower the relative risk of cardiovascular disease in some but not all studies. In contrast, recent randomized controlled trials in older postmenopausal women (e.g., Women's Health Initiative [WHI]) report an increased risk of cardiovascular disease. Emerging data suggest that these disparities in findings may be related to the timing of initiation of estrogen therapy in relation to the proximity of menopause. Subgroup analyses of the combined estrogen and progestin (EPT) arm of the WHI demonstrated a significant interaction between coronary heart disease (CHD) risk and time since initiation of EPT, with an increased risk in the early years following initiation and a decreased risk in later years. Additionally, the increased risk of CHD was observed in older but not younger perimenopausal women. High doses of oral estrogens have been reported to elevate hepatocellular enzyme levels and, less commonly, cause cholestatic jaundice. The risk for gall stones and hepatocellular adenomas has been reported to be increased in association with oral contraceptive use, and although uncommon these complications may also occur with the use of replacement doses of estrogen. Estrogen therapy also may increase the risk of urinary incontinence in older postmenopausal women. Further, most studies have suggested an increased relative risk of breast cancer after four or five years' use, similar to the risk expected if the onset of menopause was delayed for a comparable length of time. Due to the publicity surrounding the cancellation of the treatment arm of the Women's Health Initiative study that involved the administration of combined conjugated estrogens and medroxyprogesterone acetate (Prempro), we have included the following statement in the consent documents:

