
Adverse Events Related to Combined Hormone Replacement and the Results of the Women's Health Initiative (WHI): The WHI study demonstrated that continuous administration of one form of estrogen (conjugated estrogens) in combination with one form of progesterone (medroxyprogesterone acetate) is associated with an increased risk of dementia, heart attacks, stroke, blood clots, and breast cancer. Estradiol, the form of estrogen that we use in this study, is administered as a sole agent (with the exception of one week's combination with progesterone) and, consequently, we do not expect that it will

pose the increased risks observed with the chronic combination of the conjugated estrogens and medroxyprogesterone administered in the WHI study. Indeed, while the estrogen alone arm of the WHI trial was shown to be associated with an increased risk of stroke, no increased risk of either heart disease or breast cancer was observed. Estrogens may precipitate migraine headaches, and depression has also been reported to occur with the use of estrogens. In general, considering the dose and duration of treatment that we propose to use in this protocol, the risk of developing such side effects is negligible.

**Progesterone:** Progesterone and the synthetic progestins are widely prescribed, with indications including dysfunctional uterine bleeding, endometriosis, mastodynia, galactorrhea, and precocious puberty. Side effects reported in women taking progestins may include breakthrough bleeding, edema, change in weight (increase or decrease), cholestatic jaundice, rash (with or without pruritus), depression, easy fatigue and sedation, lack of initiative, and chloasma. Since progestins are often used in women with antecedent menstrual irregularity, it is not clear whether the breakthrough bleeding represents an effect of the medication or refractoriness to treatment. In the large majority of patients, menstruation occurs predictably following withdrawal of progestins and is usually more regular than in spontaneous cycles. In a recent study, an average dose of 1750 mg of oral micronized progesterone was given to 59 women with PMS for a period of three months and was well tolerated by this sample. The side effects reported on progesterone were lightheadedness, fatigue, forgetfulness, and headaches. These were very mild and caused no dropouts.

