### 3 Study Design

#### 3.1 General Design

Overview. This is an observational, case-control, single-center study using estradiol and progesterone to examine the role of frontostriatal hypoactivity in the pathophysiology of perimenopausal MDD (by assessing baseline differences between perimenopausal MDD and controls.) It will also allow us to measure frontostriatal responses to estradiol treatment in both perimenopausal MDD and control women. This study will include 6 study visits that will take place over the course of approximately 6 weeks. Participants will receive transdermal estradiol for 3 weeks and FMRI sessions will occur at baseline and at the end of the third week of estradiol administration. The procedures that will take place are outlined in **Table 1** and detailed below.

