**Table 1. Study Procedures and Timeline**

Study visit	1	2	3	4	5	6
Consent	x					
OBGYN Exam		x				
fMRI			x			x
PRT			x			x
Venipuncture		x	x	x	x	x
SCID	x					
SNAP	x					

HAM-D	x		x	x	x	x
IDAS	x		x	x	x	x
PANAS	x		x	x	x	x
MASQ	x		x	x	x	x
GCS	x		x	x	x	x
PSQI			x			x
Estradiol Rx provided			x	x	x	x
Progesterone Rx provided						x
Payment	\$100	\$30	\$150	\$35	\$35	\$150

**Participants.** Participants will include healthy, unmedicated perimenopausal women ages 44-55 either with ( $n=20$ ) or without ( $n=20$ ) current major depression.

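### Section 6 leaves estradiol out at visit 6, contrary to Table 1 and the planned combined estradiol-progesterone week: a minor dosing-text correction.

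*Combined protocol and SAP*

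**What the plan says.** Section 6, under Drug Administration, gives the dispensing visits in two sentences: "Participants will receive estradiol at study visits 3-5. Participants will receive Progesterone at visit 6". Nothing else appears in that entry.

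The other places that bear on the schedule are:

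- **Table 1 (section 3.1).** The row "Estradiol Rx provided" is marked at visits 3, 4, 5 and 6. The progesterone row is marked at visit 6 only.
- **Section 5.2, Treatment Regimen.** After three weeks of estradiol: "Women will receive an additional week of combined estradiol and micronized progesterone (200 mg/day) at the end of the study to precipitate menstruation". The same sentence appears in the Study Summary regimen and under Hormone Administration in section 3.1.
- **Section 1.4.** Estradiol "is administered as a sole agent (with the exception of one week's combination with progesterone". The protocol introduces this text with the words "we have included the following statement in the consent documents".
- **Section 1.2, on the patch.** "The period of use is 7 days". Section 5.7 adds that patches are handed out at the weekly visits.
- **Section 3.1, Overview.** "FMRI sessions will occur at baseline and at the end of the third week of estradiol administration". Table 1 puts the two scans at visits 3 and 6.
- **Study Summary.** The entry "Duration of administration" reads 3 weeks.

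**The concern.** Section 6 names what is given at visit 6, and estradiol is not in it. Someone dispensing from that entry would hand over progesterone and no patch, and the woman's last patch would reach the end of its wear time that day. Her fourth week would then be progesterone without estradiol, which differs from the regimen in section 5.2 and from what section 1.4 says participants are told in the consent documents.

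Two practical matters follow. Sections 5.9.3 and 5.9.4 call for drug reconciliation and for discrepancies to be investigated, and the protocol as it stands gives two expected patch counts per woman. The background in section 1.2 also treats estradiol withdrawal as a trigger of depression in susceptible women, and section 1.4 lists depression among reported progestin side effects. Estradiol stops under either text, so what differs is one week's timing and whether the two drugs overlap.

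**Working it through.** The protocol prints no patch count, so the check is a direct count of dispensing visits against days of cover.

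**Inputs**

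- Wear time: 7 days per patch (sections 1.2 and 5.7).
- Dispensing visits: 3, 4 and 5 under section 6; 3, 4, 5 and 6 under Table 1.
- Visit timing: visit 3 is the baseline scan and first dispensing, visits are weekly, and visit 6 closes the third estradiol week. This places visits 3, 4, 5 and 6 at days 0, 7, 14 and 21.
- Assumption: one patch at each listed visit. Section 5.7 points to this but does not give a number.

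**Need under the regimen (section 5.2)**

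3 weeks alone + 1 combined week = 4 x 7 = 28 days, or four patches.

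**Supply = number of dispensing visits x 7 days**

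| Text | Patches | Estradiol days | Days covered in week 4 | Shortfall |
|---|---|---|---|---|
| Table 1 (visits 3-6) | 4 | 4 x 7 = 28 | 7 of 7 | 0 |
| Section 6 (visits 3-5) | 3 | 3 x 7 = 21 | 0 of 7 | 28 - 21 = 7 days, one patch |

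Table 1 reproduces the regimen exactly. Section 6 falls short by 7/28 = 25% of the intended estradiol days, all of them in the combined week.

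**Effect on endpoints**

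Estradiol days before visit 6 are 21 under both texts, a difference of 0. The second scan, with its response latencies, and the last scheduled symptom ratings are at visit 6. The power statement in section 7.1 rests on change from baseline to post-treatment with 20 women per group, and no week-4 quantity enters it.

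**Which text is wrong**

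Four places state the combined week in words: the Study Summary regimen, Hormone Administration in section 3.1, section 5.2 and the consent statement in section 1.4. Table 1 shows it by scheduling both drugs at visit 6. Section 6 stands alone against them.

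**The case against.** The best reply is that the correct regimen already stands where dosing is defined, in section 5.2 and in the dispensing rows of Table 1. Section 6 is a short recap that defers to an attached flowchart for visit procedures. It does not say that progesterone is the only drug at visit 6, and it gives no patch count. The one-patch figure therefore depends on the assumption of one patch per visit. All of this is fair, and it keeps the point small. It does not reconcile the two visit lists: no available text provides for a second patch at visit 5, and section 6 does not limit itself to the estradiol-alone phase.

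A reader might go further in three ways that the documents do not support.

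- **That women actually received progesterone alone in week 4.** The flowchart and part of the material following section 5.4 could not be checked, and the documents do not report what was dispensed.
- **That the efficacy results or the power are compromised.** The endpoint data are collected by visit 6, before the two texts diverge.
- **That the 3-week duration in the Study Summary is a second contradiction.** It matches the estradiol-alone phase, and the regimen in the same summary goes on to give the fourth week.

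**Conclusion.** The inconsistency is real and section 6 is wrong as written. Read literally, and assuming one 7-day patch per weekly visit, it gives 21 rather than 28 days of estradiol and leaves the combined week without any. The shortfall is one patch per completer.

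This is a minor correction to a dosing instruction. The choice of regimen is not in dispute, the intended schedule is clear from the rest of the protocol, and no endpoint or power figure changes. It is still worth correcting, because the wrong visit number sits in the procedure entry for giving the drug and departs from the reported consent wording.

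**What to change.** In section 6, Drug Administration, change the visits in the first sentence from 3-5 to 3-6 and leave the progesterone sentence as it is. The entry then agrees with Table 1 and section 5.2: four patches, 28 days, no shortfall. Check that the attached flowchart says the same.

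Optionally, expand the Study Summary duration to 3 weeks of estradiol alone plus 1 week of estradiol with progesterone.

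The cost is one text edit, or two with the optional one. No visit, participant or analysis is added. If dispensing has followed section 6, the correction needs at most one more patch per woman who reaches visit 6. For the 40 completers planned in section 7.1 (2 x 20) that is 40 x 1 = 40 patches.
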